Following informed consent, the patient will be asked demographic and other subjective/baseline questions about their past experience with refraction and glasses dispensing(s), as well as expectations. These may be video recorded verbal conversations or paper questionnaires. Subjects may be given a wearable heart rate monitor for the remainder of the procedures.

Patients will be randomized to experience either a traditional refraction or a Vision-R800 refraction performed by a study team member (optometrist). The starting point will be the patient's habitual prescription. The refraction will be audio/video-recorded. A final prescription will be generated. Following the refraction, subjective feedback will be obtained.

Patients will be presented with a frame board (of standard, Luxotica frames) and asked to choose a frame. The necessary fitting measurements and adjustments will be made. Spectacle lenses will be manufactured for this frame using prescriptions from either the traditional refraction or the Vision-R800 refraction.

Upon arrival and verification of the edged and assembled glasses, patients will be presented with their spectacles. Spectacles will be dispensed by an experienced optician. At dispensing and at a two-week follow-up visit, subjective and objective vision testing will be completed. Subjects will be asked to wear their glasses at least 6 hours per day.

Subjects will then be randomized to the other type of refraction and all testing procedures will be repeated. All frames and lenses will be provided by the Sponsor. Between the ordering of the second pair of glasses and their dispensing, subjects will be asked to wear their habitual spectacles.

At the final visit, an investigator will show the patient the following prescriptions, in a randomized order, via the Vision-R800 phoropter, and record visual acuity and subjective ratings, while keeping the patient masked. Finally, the patient will be asked their preference for each prescription in paired comparisons, both monocularly and binocularly.

1. Habitual glasses prescription
2. Traditional refraction prescription
3. Vision-R800 refraction prescription

Primary Outcome Measures:

- Test potential claims with patients, as measured by subjective questionnaires
- Assess the benefits of the full Vision-R800 experience from refraction to lenses to the patient, as measured by subjective questionnaires

Other Outcome Measures:

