**Clinical Investigation of the VR-800 Device:
Statistical Methods and Analytic Considerations**

NCT Number: NCT04208750

Document Date: 03 FEB 2020

Statistical methods and analytic considerations

Sample size. An initial calculation was made for the continuous subjective rating data to determine the sample size required to detect an expected small effect size (0.3) using a paired samples-t-test targeting 80% power and level of significance of 5% (two-sided). This calculation indicated that a total sample size $N=90$ was required to detect an effect size of 0.3 in the paired mean difference between the Vision-R™ 800 and the standard refractions. Because several of our subjective measures were based on a comparison of proportions in the full sample ($N=90$) we also estimated the sample size needed for testing a difference in proportions of $\Delta p = 0.65 - 0.35 = 0.3$ in a paired-sample design. We found that the required sample size of $N=85$ would achieve 80% power at the two-sided 5% level of significance.

To allow for an attrition rate of 25%, we increased the larger of the two sample size estimates ($N=90$) to obtain a post-screening study sample size of $N=120$.

Overview. All analyses were performed using R v3.5.3 (The R Foundation; www.r-project.org) and SAS v9.4 (SAS Institute, Cary, NC, USA). For each outcome measure, all available data were incorporated into the statistical analyses and modeling. Although not a primary comparison, habitual lens information is included in some instances to provide additional context for comparison of the Vision-R™ 800 and standard refraction technologies data.

Refractive error. Clinically obtained measures of refractive error measures (sphere, cylinder and axis) were converted to Cartesian power vector coordinates (M, J0, and J45)(Thibos, Wheeler et al. 1997, Thibos and Horner 2001) and refractive error differences depicted graphically in three-dimensional plots, conditioned by both refraction technology and participant group. These data were summarized in terms of parameter estimates of location (i.e., mean and median) and dispersion (i.e., standard deviation, standard error of the mean, median, minimum, maximum, range and 95% confidence intervals based on quantiles of the Student's *t*-distribution). Multivariate tests were used to statistically evaluate hypotheses related to differences between the refraction technologies.

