Missingness due to COVID-19. There were two main data-related issues in this study due to the COVID-19 global pandemic and subsequent lockdown that began while the study was underway. First, because the pandemic prevented many participants from attending their final in-office visit, final subjective questionnaire responses were collected for some participants using an electronic survey. Post-hoc analyses indicated no significant differences between measures collected in-office and those collected remotely. Thus, all in-office and remotely collected data were pooled for purposes of analysis. Second, we note that differences in the final sample size of the two study groups (N=49 versus N=39 for young adults and presbyopes, respectively) are related to recruitment process at the beginning of the study rather differential drop-out during the study. Third, statistical comparisons between response proportions for the refraction technologies in the full sample remains appropriately powered. However, for conditional analyses comparing refraction methods within the young adult and presbyope subgroups, some caution is advised as the implied power is slightly under the targeted level of 80% for intermediate effect sizes.

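### The SAP's statement that full-sample response proportions stay adequately powered should exclude the masked prescription preference, which needed the final in-office visit that an unreported number of participants missed.

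*SAP*

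**What the plan says.** The SAP's sample-size section sizes the preference-type outcomes by "testing a difference in proportions of $\Delta p = 0.65 - 0.35 = 0.3$ in a paired-sample design" and concludes: "We found that the required sample size of $N=85$ would achieve 80% power at the two-sided 5% level of significance".

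The section on missingness due to COVID-19 reports that "the pandemic prevented many participants from attending their final in-office visit". It says that final questionnaire answers were taken by electronic survey for some participants and that remote and in-office data were pooled. It gives final group sizes of 49 young adults and 39 presbyopes, then states that "statistical comparisons between response proportions for the refraction technologies in the full sample remains appropriately powered". The only caution that follows concerns analyses within the two age groups.

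The protocol, under the evaluation of patient experience, describes the masked comparison: "At the final visit, an investigator will show the patient the following prescriptions, in a randomized order, via the Vision-R800 phoropter". Acuity, ratings and paired preferences (monocular and binocular) are recorded there with the patient masked. The list of patient outcome measures repeats that an investigator runs this test and that the patient is masked.

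**The concern.** A survey link can carry a questionnaire. It cannot carry a lens comparison made inside a phoropter by an investigator. The SAP describes a remote substitute for the questionnaire only, so a participant who missed the final visit has no masked preference. That preference is nevertheless a response proportion comparing the two refraction technologies, and the power sentence does not set it apart.

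This is the only comparison that the protocol describes as masked. It bears on whether a stated liking for the new technology reflects the prescription itself or the experience around it. Read literally, the SAP lets a weak masked result pass as coming from an adequately powered comparison. It also lets that result stand beside an unmasked preference taken from a larger and partly different set of people.

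**Working it through.** **Inputs.** From the SAP: proportions 0.65 and 0.35, paired; two-sided 5%; 80% power; N=85 required; final groups of 49 and 39. Not in the documents, so assumed: the number absent from the final visit (shown as a range), and that every participant states a preference.

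**Step 1: reproduce the SAP's 85.** If everyone chooses one technology or the other, the paired comparison of 0.65 with 0.35 is a one-sample test of 0.65 against 0.50:

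n = [(1.960 × 0.5 + 0.8416 × √(0.65 × 0.35)) / 0.15]² = [(0.980 + 0.401) / 0.15]² = 84.8, rounded up to 85. This matches the SAP.

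**Step 2: the margin.** 49 + 39 = 88, and 88 − 85 = 3 participants.

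**Step 3: power at the attending N.** Power = Φ[(0.15√N − 1.960 × 0.5) / √(0.65 × 0.35)]. The approximate 95% half-width at 0.65 is 1.96 × √(0.65 × 0.35 / N).

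| Absent (assumed) | N | Power | Half-width (percentage points) |
|---|---|---|---|
| 0 | 88 | 81.5% | 10.0 |
| 3 | 85 | 80.1% | 10.1 |
| 4 | 84 | 79.6% | 10.2 |
| 10 | 78 | 76.5% | 10.6 |
| 20 | 68 | 70.5% | 11.3 |
| 40 | 48 | 54.9% | 13.5 |

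**Step 4: how firm is the threshold?** The general paired formula is n = [1.960√p_d + 0.8416√(p_d − d²)]² / d², where p_d is the share stating a preference and d the difference in proportions. Step 1 is the case p_d = 1, d = 0.30.

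- 10% with no preference and a 65:35 split among the rest (p_d = 0.9, d = 0.27): n = 94.5, so 95.
- 20% with no preference, same split (p_d = 0.8, d = 0.24): n = 106.6, so 107.
- 20% with no preference, difference held at 0.30 (p_d = 0.8): n is about 67.
- Exact binomial test with no ties: power at 88 is already 79.7%.

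The threshold of 85 therefore moves in both directions with assumptions that the SAP does not state.

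**The case against.** The strongest reply is that the sentence was never meant to cover the masked test. It speaks of the full sample, and an outcome missing for non-attenders is not a full-sample outcome. The SAP does not name the masked preference, and its section on subjective preferences can be read as questionnaire content. The overview allows N to vary, since all available data are used for each outcome. This has some force, but in context the full sample is contrasted with the two age groups, not with outcomes that lack data. No N is given for the masked preference anywhere, so the reader cannot tell that it is excluded.

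Second, the SAP reports every categorical measure with a 95% interval and assesses preferences with Bayes factors. An interval at the attending N would show some of the lost precision, and power is only a design benchmark here. That stands and lowers the stakes. It does not make the sentence accurate, and it does not give masked and unmasked results a common denominator.

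Three stronger readings are tempting, and the documents do not support them.

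- *The main results are underpowered.* Both primary outcomes in the protocol are measured by questionnaire, which could be answered remotely. At 88 respondents the SAP's claim holds on its own formula.
- *Power for the masked preference is shown to be below 80%.* The number absent is not reported. That the 88 include remote responders is inferred from the pooling; if they were all attenders, the shortfall would disappear.
- *A fourth absence is a real breaking point.* The step from 80.1% to 79.6% is immaterial, and Step 4 shows how far the threshold depends on the method and on ties.

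**Conclusion.** The point holds in limited form. The power statement is sound for response proportions with about 88 respondents, and too broad as applied to the masked paired preference. For that outcome the margin over the SAP's own requirement is 3 participants, while the SAP itself reports that many missed the visit, so the claimed power is very unlikely to apply. The size of the shortfall is unknown: negligible for a handful of absences, about 5 points below 81.5% with 10 absent, about 11 points with 20 and about 27 points with 40.

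This rests on three assumptions: the 88 include people who answered remotely, no substitute for the phoropter test was used, and every participant stated a preference. It is a matter of reporting and interpretation for a masked secondary comparison, not a defect in the primary analysis.

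**What to change.** 1. In the COVID-19 section, limit the power statement to outcomes with at least 85 respondents.
2. For the masked preference, give the number who attended the final visit and restate the power or interval width at that N.
3. Tabulate the unmasked preference in those same attenders, beside the all-responder result, so that masked and unmasked findings share one denominator.

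The cost is a few lines of SAP text, one extra tabulation from data already collected, and a less favourable stated power for the masked outcome.

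Moving the masked session to an earlier visit is not recommended. Comparing prescriptions head to head before the second pair has been worn could influence the later questionnaires, which carry the primary outcomes. Nothing shows that an earlier in-office visit was less exposed to the lockdown, and the SAP's past tense indicates that data collection is complete.
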